#### 2.2 Regional Finding

A study from Korea mentioned 38% (n=342) caregiver of children bearing cancer had anxiety, with 5 % of them had severe anxiety. 82% (n=737) caregiver had depression, and 16% abode severe depression of cancer patient. The predicted anxiety level of family caregiver was 9.22 times higher with poor Quality of life (QOL), for burdensomeness 3.44 times higher for degree of disturbance and 2.12 times higher for financial concerns. There are many evidences of nursing intervention effect on anxiety and depression other than chemotherapy side effect management. A study from Turkey mentioned the effect of multimedia nursing education for cardiac care on anxiety and depression score from  $6.1\pm0.7$  and  $5.4\pm0.6$  reduced to  $1.9\pm0.2$ and  $1.9 \pm 0.3$  [37]. In Iran effect of nurse led telephonic follow on anxiety and depression for hemodialysis patients was studied [42] Other studies provided evidences of family anxiety reduction in cardiac care [23, 29, 34, 38], during electroconvulsive therapy [33], elderly care [22] and for laparoscopic cholecystectomy [41].. Another study from Korea also mentioned the effect of nursing intervention on anxiety during laparoscopy hysterectomy [58]. A study from Azerbaijan mentioned positive effect of nursing intervention on anxiety during endoscopy [53] and from Egypt mentioned positive effect of nursing intervention on anxiety during MRI procedures [32]. Studies from China also mentioned the effect of nursing intervention on anxiety level for peptic ulcer [44], breast cancer [40], tooth extraction [43] and laparotomy [39].

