#### 2.3 Local findings:

A study from Rawalpindi revealed that 10%-25% participant reported anxiety and depression during chemotherapy and 16% had anxiety and 27% had depression [4]. Myeloid leukemia was commonly diagnosed in younger age but mostly reported in chronic phase [59]. A study from Lahore mentioned that 56% parents had depression, higher in mothers specially those who were low educated and had poor socio-economic class [5]. A study from Karachi mentioned caregiver stress related to cancer patients, 17% mild, 34% moderate and 49% had severe stress. It was also concluded that caregiver stress for cancer patient had significant association with caregiver age, relationship with child, female gender and longer duration of care [49]. A study was conducted in Karachi to identify the psychological need of parents of children disposed with cancer and found that correct and adequate information through education is necessary for parents [60].

We fail to find study both regional and locally focusing this concept.

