#### 3.13.2 Independent Variable:

The independent variable was mentioned as socio-demographics and other information in **Annexure-I**. It included (1) Sectioned (A), Personal information focusing Child Age, Child gender, Primary Care taker area of residence, (2) Section (B), Socioeconomic and educational status of Childs caretaker focusing Occupation, Level of education, Employment status, Income per month and Treatment Expenses. (3) Section C, Cancer Information focusing Diagnoses, Type of cancer, Stage of cancer, treatment being sought, Duration of Chemotherapy, Date of diagnoses, Duration of diagnoses, Family History of cancer and Number of cancer patients in the family of the patient other than this case. (4) Section (D), Pain scale focusing Pain felt by the child at that moment and (5) Section (E), General information related to Anxiety and depression focusing, Caregivers awareness of whether he or she was anxious and depressed? Did caregivers taken any treatment sought for his anxiety and depression? Whether any health professional advices the Caregivers? and Do caregiver had smoking habits?

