# Factor associated with Anxiety and depression:

Nearly, 42.9% parents had smoking habits, while 57.1 % did not have smoking habit. The baseline data of parents along with their child are shown in Table 1.

	Total	Intervention	Control	
Section A: Personal information	n=77 (100%)	n=41 (100%)	n=36 (100%)	Chi-Square
				P-Value
1. Child Age:	-	-	-	
2-4years	24(31.2)	13(31.7)	11(30.6)	0.98
5-7years	18(23.4)	10(24.4)	8(22.2)	
8-12 years	24(31.2)	12(29.3)	12(33.3)	
13-18 years	11(14.3)	6(14.6)	5(13.9)	
2. Child Gender:	50/54.0	0 4 ( 5 0 5 )		
Male	50(64.9)	24(58.5)	26(72.2)	0.20
Female	27(35.1)	17(41.5)	10(27.8)	
3. Primary Care Giver:	(0/00.2)	20(02.7)	20(02.2)	0.00
Mother/Father	68(88.3)	38(92.7)	30(83.3)	0.20
Other	9(11.7)	3 (7.3)	6 (16.7)	
4. Residency/Locality:	20(2( 4)	17(41.5)	11(20.6)	0.22
	28(36.4)	1/(41.5)	11(30.6)	0.32
Non-Local	49(63.6)	24(58.5)	25(69.4)	A1 • A
Section B: Socioeconomic and	N=77 (100%)	Intervention	Control	Chi-Square
educational status of Childs care taker		n=41 (100%)	n=36 (100%)	P-Value
5. Occupation	12(54.4)	24(59.5)	19(50)	0.74
	42(54.4)	24(58.5)	18(50)	0.74
Shopkeeper	17(22.1)	8(19.5)	9(25)	
Other	18(23.4)	9(22)	9(25)	
6. Level of education		11(2(0))	11(20.0)	0.00
	22(28.6)	11(20.8)	11(30.6)	0.80
School Education	33(42.9)	1/(41.5) 12(21.7)	16(44.4)	
Higher Education	22(28.6)	13(31.7)	9(25)	
7. Employment status	40((2, ())	29((9.2)	21(59.2)	0.26
Daily wages	49(63.6)	28(08.3)	21(58.5)	0.30
Nonthly Salary	28(36.4)	13(31.7)	15(41.7)	
8. Income per month (Rupees)	20(27.7)	12(20.2)	17(47.2)	0.10
less than 10,000	29(37.7)	12(29.3)	1/(4/.2)	0.10
More than 10,000	48(62.3)	29(70.7)	19(52.8)	
Section C. Concer Information	N = / / (100%)	n=41 (1009/)	Control	D Voluo
0 Diagnosos		II-41 (10070)	II-30 (100 % )	F-value
J. Diagnoses	51(66.2)	28(68.2)	22(62.0)	0.59
Othora	31(00.2) 26(22.8)	20(00.3) 12(21.7)	23(03.9) 12(26.1)	0.58
10 Family History of cancor	20(33.8)	15(51.7)	15(50.1)	
No.	70(00.0)	34(82.0)	33(01.7)	0.25
	70(90.9)	7(17.1)	3(83)	
Section D: Pain scale (Visual analog	N=77 (100%)	Intervention	S(0.5)	Chi Sauara
scale)		n=41 (100%)	n=36(100%)	P_Voluo
11 Pain falt by the child			II-30 (100 /0)	I - Value
No	49(63.6)	23(56.1)	26(72.2)	0.14
Ves	28(36 /)	18(43.0)	10(27.8)	
Section F: Factor associated with	N=77(100%)	Intervention	Control	Chi-Square
Anxiety and depression		n=41 (100%)	n=36(100%)	P-Value
12. Do parent have smoking habits?			1 20(10070)	I - V aiut

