8.	Income per month (Rupees)	0.32	0.07	0.92
9.	Diagnoses	0.97	0.77	0.81
10.	Family History of cancer	*0.02	0.20	0.77
11.	Pain felt by the child	0.12	0.11	0.51
12.	Do parent have smoking habits?	0.92	0.88	0.50
	Significant Association (P-V	/alue <0.05)		

 Table 5 : Association of Socio demographical features with pre-depression, pre-anxiety and pre-stress

The significant association has been identified between child age and pre-anxiety of parents, Occupation and pre-depression of parents and family history of cancer and pre-depression of parents. It is further identified that there is significantly 4 times more likely to have no Anxiety at the time of admission (pre-anxiety), if the child age is < 4 year as compared to the child age > 4 years [OR=4.1, 95%CI(1.0-16.2),P-Value=.042] Moreover, found that there is significantly 20% less likely to have no depression at the time of admission (pre-depression), if Family history has cancer as compared to no history of cancer patient in family [OR=0.20, 95%CI(.047-.880),P-Value=.033]. No association was found with other variable.

Since, almost all variables produced insignificant effect on the outcome variables at three stages of observations. Therefore, these variables were not proceeded for multivariable analysis.

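### Section 4.3.3 rules out covariate adjustment on a non-significance screen shown only at baseline; a post-hoc adjusted arm comparison should stand beside the unadjusted one

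*Combined protocol and SAP*

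**What the plan says.** Section 3.14 plans a repeated-measures ANOVA of the DASS scores and names no covariates. Table 4 accordingly gives unadjusted between-arm p-values: 0.012 for depression, 0.172 for anxiety and 0.012 for stress.

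The last paragraph of section 4.3.3 gives the reason for going no further: "Since, almost all variables produced insignificant effect on the outcome variables at three stages of observations". It continues: "Therefore, these variables were not proceeded for multivariable analysis".

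The table behind this is Table 5, titled "Association of Socio demographical features with pre-depression, pre-anxiety and pre-stress". It holds chi-square p-values for 12 characteristics against three baseline outcomes. The income row reads "Income per month (Rupees) 0.32 0.07 0.92", for depression, anxiety and stress in turn. Section 3.13.2 lists further variables collected, among them "Stage of cancer, treatment being sought, Duration of Chemotherapy, Date of diagnoses", which appear in neither Table 1 nor Table 5.

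The literature review names socio-economic position as relevant. Section 2.3 cites a Lahore study in which "56% parents had depression, higher in mothers specially those who were low educated and had poor socio-economic class". Section 2.2 cites a Korean survey in which caregiver anxiety was "2.12 times higher for financial concerns".

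**The concern.** There are three separate problems.

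- **The reason does not match the evidence.** The text claims no effect at all three measurement points, but nothing is shown for day 14 or day 28, the visits on which the arms are compared after the intervention.
- **The rule is weak, and was not followed.** A univariable p-value in 77 parents cannot establish that a characteristic has no bearing on the later score, and it says nothing about imbalance between arms. Three characteristics did pass the 0.05 screen and were dropped with the rest.
- **The comparison is of completers.** Of 100 randomised, 77 were analysed, with losses of 9/50 and 14/50. Imbalances in Table 1 may come from attrition as well as chance, so randomisation alone is a weaker assurance than usual.

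At stake is how well the unadjusted arm difference supports chapter 5, which attributes the reductions in depression and stress to the intervention.

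**Working it through.** **1. What the screen contains.** Table 5 has 12 × 3 = 36 tests, all at baseline. Three are below 0.05: child age with anxiety (0.031), occupation with depression (0.017) and family history with depression (0.02). By chance alone 36 × 0.05 = 1.8 would be expected, so three is not remarkable, but it is not none.

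**2. How much the screen could detect.** Chi-square tests on baseline status imply the Yes/No categories of section 3.13.1. At baseline 65/77 (84.4%) had depression (Table 3). Compare the 29 lower-income with the 48 higher-income parents, and assume a true 15-point difference in prevalence (93.75% vs 78.75%):

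- null SE = √[0.844 × 0.156 × (1/29 + 1/48)] = 0.085
- alternative SE = √[0.9375 × 0.0625/29 + 0.7875 × 0.2125/48] = 0.074
- power ≈ Φ[(0.15 − 1.96 × 0.085)/0.074], roughly 40%

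The same calculation for baseline anxiety (67.5%) gives about 27%.

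**3. Reproducing the income row of Table 1.** Below 10,000: 12/41 (29.3%) vs 17/36 (47.2%). Pearson chi-square without continuity correction is 2.63, p = 0.105, matching the stated 0.10. The difference is 0.4722 − 0.2927 = 0.180. The standardised difference is 0.180/√[(0.2927 × 0.7073 + 0.4722 × 0.5278)/2] = 0.38.

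**4. Other rows of Table 1, by the same formula.**

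| Characteristic | Intervention | Control | Std. difference | More common in |
|---|---|---|---|---|
| Low income | 29.3% | 47.2% | 0.38 | control |
| Child in pain | 43.9% | 27.8% | 0.34 | intervention |
| Daily wages | 68.3% | 58.3% | 0.21 | intervention |
| Labour occupation | 58.5% | 50.0% | 0.17 | intervention |
| Uneducated | 26.8% | 30.6% | 0.08 | control |

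Family history is left out because its arm counts for Yes (7 + 3 = 10) do not add up to the total (7).

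**5. Size of an income effect at day 28.** Tilt = 0.180 × assumed effect of low income on the score; the documents give no such effect. The depression difference is 6.11 − 2.63 = 3.48 (Table 2).

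| Assumed effect | Tilt | Share of 3.48 | Share of intervention-arm variance |
|---|---|---|---|
| 2 points | 0.36 | 10% | 9% |
| 4 points | 0.72 | 21% | 37% |
| 6 points | 1.08 | 31% | 84% |

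The last column is 0.293 × 0.707 × effect², divided by 2.98² = 8.88. At 6 points, income alone would explain 7.45 of 8.88, which is not realistic. Erasing the difference would take 3.48/0.180 = 19.4 points.

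**6. Effect on the reported p-values.** The between-arm p-value is consistent with a contrast averaged over the three visits. For depression this is (0.87 + 3.28 + 3.48)/3 = 2.54; with p = 0.012 on 75 degrees of freedom (t = 2.575), SE = 0.99. For stress it is (0.04 + 3.98 + 3.95)/3 = 2.66, SE = 1.03. Subtract the tilt and hold the SE fixed:

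- A 2-point income effect gives p ≈ 0.030 for depression and 0.029 for stress.
- Significance is lost only above about 3.2 points (depression) or 3.3 points (stress), about 0.74 SD of the averaged score.
- The baseline depression p-value for income (0.32) corresponds roughly to 0.23 SD, or 1.0 point: tilt 0.18, p ≈ 0.019. Table 5 gives no sign; if reversed, p ≈ 0.007.
- For stress (baseline p = 0.92) the result stays at about 0.013.

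**The case against.** The strongest reply is that nothing planned was dropped. Section 3.14 names no covariates, an unadjusted comparison of randomised arms is valid, and adjustment is mainly a matter of precision. The sentence in 4.3.3 also follows directly on odds ratios for baseline anxiety and depression, so the analysis declined may be the risk-factor analysis and not the arm comparison. Both points are fair. They make this a request for a supporting analysis and not a charge that the main one is invalid. They do not rescue the stated reason, and the validity argument is weaker for 77 completers of 100.

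The imbalance is also ordinary: with 12 independent baseline tests, a smallest p-value of 0.105 or less arises with probability 1 − 0.895^12 = 0.74. That stands.

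A reader might go further and infer that control is simply the poorer arm, so that the unadjusted result is tilted towards the intervention. The documents do not support this. Labour occupation, daily wages and child's pain are more common in the intervention arm and, if they raise distress, would work against it. The Lahore study concerns depression and the Korean finding anxiety; neither speaks to income and stress. Baseline scores show no consistent tilt either: stress is 16.63 vs 16.67, anxiety is higher in the intervention arm (11.9 vs 10.72), and depression differs by 0.87. The stress and depression gaps open mainly after baseline.

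Finally, choosing covariates now is itself data-dependent. That is correct, and it governs how the adjusted analysis must be labelled.

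**Conclusion.** The concern holds in a limited form. The reason given in 4.3.3 is not supported by Table 5, and significance screening is a poor basis for deciding on adjustment. Income differs between the analysed arms by 18 percentage points (standardised difference 0.38). Read with the Lahore study, that one imbalance would favour the intervention on depression, but the net direction of all imbalances is unknown.

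Under an assumed 2-point income effect the contribution is about 0.36 of 3.48 points (10%) at day 28. Depression and stress remain significant for income effects up to about 0.74 SD. These figures rest on an assumed income effect, on one covariate at a time and on an SE left unchanged by adjustment; a true adjusted estimate needs the patient data. A claim that adjustment would overturn the depression or stress result does not follow from the documents. The value of the change lies in a sounder justification and a better-supported comparison.

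**What to change.** 1. In 4.3.3, remove non-significance as the reason for not adjusting. State that the arm comparison in 3.14 had no planned covariates.
2. Delete the reference to three stages of observation, or show the day-14 and day-28 associations.
3. Report, beside the unadjusted result, the arm difference with confidence interval at day 14 and at day 28 for each DASS outcome. Adjust for the baseline score of that outcome and for covariates chosen on prognostic grounds, whatever their p-values: income and level of education, with occupation as a reasonable addition.
4. Label this a post-hoc sensitivity analysis. Do not write it into 3.14 as though it had been planned.

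**Cost.** The income, education and occupation rows of Table 1 each sum to 77, so no parent is lost. Baseline score (1), income (1) and education (2) use four degrees of freedom, and occupation two more, out of about 75. The remaining drawback is that the covariates are chosen after the data were seen, which is why the label matters.

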#### **CHAPTER 5: DISCUSSION**

Parents are the primary care giver of the children. If parents will be in anxiety, so it will be difficult for them to manage side effect of chemotherapy. The main purpose of this study was to measure the impact of multimedia education, booklet providence and telephonic follow-up on parent's anxiety, depression and stress. As far as we know, the study is first of its kind that was conducted in Karachi Pakistan focusing this concept. We found significant reduction in depression and stress because of MBT intervention while anxiety was not significantly different between study groups.

#### **Epidemiology of Pediatric cancer:**

Large number of people are affected with cancer worldwide, leading major health problem of Pakistan [1, 2]. Approximately 8,000 children under 18 years of age are being diagnosed on yearly basis. In our study it was found that highest proprtion of patients were diagnosed with Leukemia (blood cancer) followed by Lymphoma (cancer of lymph gland), Similarly, one of the study from Pakistan also reported that Leukemia and Lymphoma were higher among children [2, 3]. The prevalence of leukemia is similarly higher in this study.

#### **Depression Anxiety and Stress among parents:**

In this study it was found that 84.4% parents had depression, 67.50% parents had anxiety and 55.50% parents had stress below normal range at baseline. The reason of mentioned in the literature that anxiety in parents was due to unawareness about chemotherapy side effect, lack of knowledge about disease, lack of knowledge above side effect management [4, 11, 16, 17, 19-21]. The findings are similar to this study, as mostly parents were unaware about the disease and management.

#### MBT as Nursing Intervention to reduce Anxiety Depression and stress:

In our study randomized control trial was done in which intervention group received multimedia education on chemotherapy and side effect management along with routine care and the control group received verbal instruction as routine care of hospital. The anxiety level was measure at 2-week differences up to 1 month and found that large no of parents reported anxiety in control group after 1 month as compared to experimental group. Similarly study was conducted by Williams and Schreier (2005) and reported larger number of patient in control group reported anxiety as compared to experimental group significantly. [26]. Another Malone (2007) and mentioned that education help in reduction of anxiety [25]. In our study it was found that parent who came at Department of Pediatric Oncology at Indus hospital, Karachi have the considerably highest pre-scores of anxiety, depression and stress.

Susan Swanson, 2008 mentioned that almost 50% cases diagnosed with cancer reported the symptoms of anxiety [51]. Similar in this study we have reported slightly higher Prevalence possibly due to study setting differences. Study from USA mentioned that, the caregiver of children diagnosed with cancer had 44% greater stress as compared to 24% parents of healthy children [47] According to National Comprehensive Cancer Network (NCCN) guideline, anxiety management related to chemotherapy and side effect management was the primary responsibility of oncology team including oncology nurse [16]. Similarly, the responsibility was assigned to physician, nurses and other paramedics. In our study it was found that almost 68% parents had anxiety and 84% caregiver had depression. Similarly, a study from Korea mentioned lower percentage that 38% caregiver had anxiety and 82% caregiver had depression [48]. In our study the effect of multimedia nursing education about chemotherapy and side effect management imparted significant reduction in anxiety (i.e. from  $11.35 \pm 6.72$  which reduced to 2.98 ± 3.23) in 1 month and in depression score (i.e. from  $15.82 \pm 6.6$  reduce to 4.26  $\pm 4.36$ ) in 1 month. This is similar to a study from Turkey that mentioned the significant

reduction of multimedia nursing education for cardiac care on anxiety and depression score from  $6.1\pm0.7$  and  $5.4\pm0.6$  reduce to  $1.9\pm0.2$  and  $1.9\pm0.3$  respectively [37]. In Iran significant effect of nurse led telephonic follow on anxiety and depression for hemodialysis patients were reported [42], evidences of family anxiety reduction in cardiac care [23, 29, 34, 38], during electroconvulsive therapy [33], elderly care [22], laparoscopic cholecystectomy [41], laparoscopy hysterectomy [58], endoscopy [53] MRI procedures [32], peptic ulcer [44], breast cancer [40], tooth extraction [43]and laparotomy [39] correspondingly supported the procedure for multimedia education and telephonic follow up. In this study we found that 30 minutes of education about chemotherapy and side effect management was enough for education to parents. In a European study they recommended 20 minutes of multimedia education [55].

We consider ourselves successful to report that our study focused on effect of nursing led education on chemotherapy and side effect management on parent's anxiety depression of children undergoing chemotherapy for the first time at local level in Pakistan. In literature we failed to find any study focusing this concept. Our study from Karachi reported 2 time higher parental anxiety and depression as compared to a study from Rawalpindi reported that 10-25% participant reported anxiety and depression during chemotherapy and 16% had anxiety and 27% had depression [4]. A study from Lahore mentioned that 56% parents had depression, higher in mothers specially those who were low educated and had poor socio-economical class. Another study mentioned that myeloid leukemia was commonly diagnosed in younger age but mostly reported in chronic phase [5, 59]. A study from Karachi mentioned caregiver stress related to cancer patients, 17% mild, 34% moderate and 49 % severe stress, mentioned that caregiver stress for cancer patient had significant association with caregiver age, relationship with child , female gender and longer duration of care [49]. The findings from our study showed that implementing MBT intervention would help to reduce depression, anxiety and stress in our setup.

This procedure adopted in this study was supported by the literatures that written material about chemotherapy side effect management is the responsibility of oncology nurses [11, 18, 24-26]. The main content of our education focused chemotherapy and side effect management. In literature it was further mentioned that education related to side effect management reduces anxiety of the patient [8, 9, 11, 15, 16, 19, 20, 27, 28, 46]. Using multimedia education for the reduction of anxiety was also found in mammography, MRI, ECT, cardiac surgeries, gynecological laparotomy, laparoscopic cystectomy, hemodialysis, teeth removal and peptic ulcer disease.[23, 29-45]. Anxiety and depression were more common due to lack of infrastructure in Pakistan [4]. Therefore, strategies like MBT intervention should be derived to reduce such psychological disorders in Pakistan especially among cancer patients and their caregivers.

